14.2. Sample Size/Accrual Rate

A total of 38 evaluable patients will be needed to meet the primary endpoint. Sample size will be inflated to 42 patients to account for unevaluable patients. Accrual duration is expected to be

21 months (accrual rate of 2 patients per month) with additional follow-up of 6 months required to reach full event information.

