8. STUDY CALENDAR

Baseline evaluations are to be conducted within 3 weeks prior to start of protocol therapy. Subsequent evaluations should be carried out on Day 1 of subsequent cycles (+/- 3 days) every 12 weeks from Cycle 46 on. Radiographic evaluations including bone and abdominal/pelvic CT scans should be conducted at baseline and every 24 weeks from Cycle 46 on.

| | Pre- Study | Cycle 1 Day 1 ^x | Cycle 2 to Cycle 45, Day 1 ^x | Day 1 Cycles ≥ 46, Every 12 Weeks ^x | Off Study ^b |
|---|---------------|-------------------------------|---|--|------------------------|
| Treatment Schedule: | | | | | |
| Tivozanib | | X (days 1-21) | X (days 1-21) | X (days 1-21) | |
| Enzalutamide | | X (Days 1-28) | X (days 1-28) | X (days 1-28) | |
| Informed consent | X | | | | |
| Demographics | X | | | | |
| Medical/Interval history | X | X | X | X | X |
| Concurrent meds | X | X | X | X | X |
| Physical exam | X | X | X | X | X |
| Vital signs/ BP | X | X | X | X | X |
| Performance status | X | X | X | X | X |
| Serum PSA | X | | X | X | X |
| PT, PT/INR, and PTT | X | | | | |
| CBC w/diff, plts | X | X | X | X | X |
| Serum chemistry ^a | X | X | X | X | X |
| Serum testosterone | X | | | | |
| Thyroid Function (TSH only) | X | | X (odd cycles) | X | |
| Urinalysis (urine protein only) | X | X | X | X | X |
| Chest xray | X | | as clinicall | y indicated | |
| Bone scan and abdominal/pelvis CT scans | X | Rep | Repeat scans every 24 weeks | | X ^c |
| EKG | X | | | | |
| Adverse Event Evaluation | X | Х | | | -X |
| Survival follow-up | | | | | X ^d |

x: ± 3 days for treatment or assessment requirement

MEASUREMENT OF EFFECT

a: Sodium, potassium, chloride, BUN, creatinine, glucose, albumin, total protein, total bilirubin, alkaline phosphatase, SGOT [AST], SGPT [ALT]

b: Off-study evaluation should occur within 30 days after the last dose of study treatment c: Post-treatment scans will be performed if an assessment has not been performed within the prior 6 weeks

d: Follow for survival information every 3 months until death, up to 2 years after discontinuing therapy, or patient lost to follow-up

The primary endpoint of the study is progression free survival (PFS). Secondary clinical endpoints will include safety, overall survival, time to PSA progression, PSA response rate and objective response rate.

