14. STATISTICAL CONSIDERATIONS

14.1. Study Design/Endpoints

The phase 2 study will evaluate the efficacy of enzalutamide and tivozanib in patients with mCRPC. The primary endpoint will be progression free survival (PFS), defined as the time from registration to the earlier of progression (radiographic or clinical) or death and, if censored, the date of last disease evaluation. Based on phase 3 data, the median PFS with enzalutamide alone in chemotherapy naive mCRPC is 14 months. The hypothesis is that the addition of tivozanib will significantly enhance efficacy. An improvement of 60% to a median PFS of 22.4 months will be considered worthy of further study. Assuming exponential distribution, this implies a hazard ratio (HR) of 0.625 relative to historical control (hazard rate from 0.0495 to 0.0309). Using a one-sample exponential test, there will be 80% power to demonstrate a 60% improvement at a one-sided Type 1 error rate of 10% with enrollment of 38 patients and 20 PFS events.

Because this combination has not been previously tested, a safety run-in will be conducted at the outset of the trial. After the first 3 patients are enrolled, accrual will be held until all three patients complete the first 1 month of treatment. Additionally, after a total of 10 patients are enrolled, these patients will be analyzed for safety and toxicity by the DSMC. If any treatment-related, expected or unexpected grade 3 or higher adverse events occur during the first month of treatment in the first 3 patients, or if the rate is >30% among the first 10 patients during the first month of treatment, further accrual will be halted for reconsideration of the appropriateness of the dosing schedules.

The table below gives the probability of observing 1 or more toxicities among the first 3 patients or 3 or more among the first 10 patients given different true underlying toxicity rates.

| True toxicity rate | 1% | 10% | 20% | 30% | 40% | 50% |
|--|--------|-------|-------|-------|-------|-------|
| Probability of Stopping Early (≥ 1/3) | 0.030 | 0.271 | 0.488 | 0.657 | 0.784 | 0.875 |
| Probability of Stopping Early (≥ 3/10) | <0.001 | 0.070 | 0.322 | 0.617 | 0.832 | 0.945 |

Thus, if the true underlying proportion of toxic events is 30% at the current dosing schedules, there is a greater than 60% chance of stopping early.

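### The 6 months of post-accrual follow-up in Section 14.2 yields about 15–16 PFS events under the 22.4-month alternative, not the 20 required; about 11–14 months are needed

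*Combined protocol and SAP*

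**What the plan says.** Section 14.1 sets the comparison. For the null it states that "the median PFS with enzalutamide alone in chemotherapy naive mCRPC is 14 months"; for the alternative, "An improvement of 60% to a median PFS of 22.4 months will be considered worthy of further study". PFS is taken as exponential, so the hazard ratio is 0.625, with monthly hazards of 0.0495 and 0.0309. The power statement reads "Using a one-sample exponential test, there will be 80% power to demonstrate a 60% improvement" at a one-sided 10% error rate, "with enrollment of 38 patients and 20 PFS events".

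Section 14.2 turns this into a timeline. It asks for 38 evaluable patients, adds that "Sample size will be inflated to 42 patients to account for unevaluable patients", and gives the accrual duration as "21 months (accrual rate of 2 patients per month) with additional follow-up of 6 months required to reach full event information".

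The only event count in the plan is the 20 PFS events, so that is what full event information must mean. Section 14.2 does not name the hazard behind the 6 months. No section says whether the primary analysis is triggered by the 20th event or by the calendar.

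**The concern.** The 80% power is claimed under the alternative, where events arrive more slowly than under the null. A follow-up period described as required to reach the event target should therefore hold under the alternative, or say that it does not. With a 22.4-month median, 21 months of accrual and 6 more months, many patients will have been observed for well under one median, so 20 events out of 38 looks too many.

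What is at stake depends on how the sentence is used. If it is only a forecast, the trial's duration is understated in the scenario the trial is designed to detect. If month 27 is taken as the analysis date, the primary test runs on fewer events than planned and with less than the stated power.

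**Working it through.** **Inputs.** From Section 14.1: medians 14 and 22.4 months, exponential PFS, one-sided error 10%, 38 patients, 20 events. From Section 14.2: 42 enrolled, accrual A = 21 months, follow-up F = 6 months. The plan gives no dropout rate for PFS, so none is assumed. Both 38 and 42 are carried through, because Sections 9.1.1 and 14.4 define evaluability for response and toxicity but not for PFS.

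**1. The plan's event target reproduces.** With d events, 2λT follows a chi-square distribution with 2d degrees of freedom, where T is total time at risk. At d = 20 and HR 0.625 the exact power is 79.9%. The normal approximation on the log-hazard scale gives d = ((1.2816 + 0.8416) / ln 0.625)² = 20.4. The 20 events, the 10% error and the event-based 80% power are correct.

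**2. Probability of an event by month 27.** With uniform accrual,

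P = 1 − [exp(−λF) − exp(−λ(A+F))] / (λA).

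- Alternative, λ = ln 2 / 22.4 = 0.03094: P = 1 − (0.8306 − 0.4337) / 0.6498 = 0.3892.
- Null, λ = ln 2 / 14 = 0.04951: P = 1 − (0.7430 − 0.2627) / 1.0397 = 0.5380.

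| | 38 patients | 42 patients |
|---|---|---|
| Expected events at month 27, alternative | 14.8 | 16.3 |
| Binomial chance of at least 20, alternative | 6.0% | 15.9% |
| Expected events at month 27, null | 20.4 | 22.6 |

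**3. Follow-up needed.** Solving n × P = 20 for F:

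| Months after accrual ends | 38 patients | 42 patients |
|---|---|---|
| Alternative | 14.2 | 11.0 |
| Null | 5.5 | 3.5 |

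Under the alternative, the simulated time of the 20th event after accrual ends has mean 13.8 and median 13.3 months with 38 patients, and mean 10.6 and median 10.3 months with 42.

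**4. Where 6 months would suffice.** Solving n × P = 20 for the median at F = 6 gives 14.5 months with 38 patients and 16.9 months with 42. The corresponding hazard ratios are 14/14.5 = 0.97 and 14/16.9 = 0.83, both far from 0.625.

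**5. Another reading of accrual.** If only 38 patients are enrolled at 2 per month, accrual takes 19 months. The alternative then gives 14.1 events at 6 months, and 20 expected events need 15.1 months.

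**6. Power if the analysis is fixed at month 27.** Simulation with 400,000 runs per hazard:

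| Test | 38: power (actual error) | 42: power (actual error) |
|---|---|---|
| Score | 73.4% (9.0%) | 76.8% (9.0%) |
| Wald, log hazard | 73.2% (8.9%) | 76.6% (8.9%) |
| Likelihood ratio | 75.5% (10.1%) | 78.6% (10.0%) |
| Calibrated to exactly 10% | 75.3% | 78.6% |

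A Wald test on the hazard scale shows 79.0% or 81.6%, but its actual error is 11–12%, so that gain is not real.

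**The case against.** The strongest reply is that 6 months is not a miscalculation. With 38 patients, 21 months of accrual and the 14-month null it gives 20.4 events, which matches the target. Section 14.2 names no hypothesis, and its wording can be read as a forecast of when an information target is met. On that reading the analysis waits for 20 events and the test keeps its power. Other sections fit this: treatment continues to progression (Section 5.4), and the Section 8 calendar has evaluations "every 12 weeks from Cycle 46 on". Cycle 46 starts 45 × 28 = 1,260 days, about 41 months, into treatment. Even on the fixed-date reading, the calibrated loss against the exact 79.9% is only 1.3 points with 42 patients and 4.6 points with 38.

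Much of this stands. The figure probably came from the null hazard, an event-driven analysis is unharmed, and the power loss at month 27 is modest. It does not rescue the sentence. The 6 months is called required without qualification. Under the hypothesis on which the power is claimed, that fails in about 84% (42 patients) to 94% (38 patients) of trials. The plan also never states that the analysis is event-driven.

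A further objection is that uniform accrual, no dropout and continuous detection are idealised. That is true, but the accrual hold in the safety run-in, loss to follow-up, scans at intervals and confirmation of radiographic progression would lengthen the time to 20 events rather than shorten it.

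**Conclusion.** The follow-up statement is wrong as written. At the 22.4-month median, month 27 is expected to deliver 14.8 events (38 patients) or 16.3 (42), a shortfall of about 4–5 events. Reaching 20 takes about 14 or 11 months after accrual ends, so the stated period is 5–8 months short. No reading of the patient number or accrual period makes 6 months sufficient under the alternative.

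The event target, error rate and event-based power are correct. The effect on power depends on a trigger that the plan does not state: none if the analysis waits for 20 events, or a fall to about 73–76% (38) or 77–79% (42) if it is fixed at month 27. These figures assume exponential PFS, uniform accrual over 21 months and no dropout. Confidence in the arithmetic is high.

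**What to change.** Restate the follow-up sentence in Section 14.2 and name the trigger, for example:

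> The primary analysis takes place when 20 PFS events have occurred. Under the 22.4-month alternative, with uniform accrual and no dropout, this is expected about 14 months after accrual ends with 38 evaluable patients, or about 11 months if all 42 contribute.

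If month 27 is to be kept as the cut-off, state instead that about 15–16 events are expected under the alternative and replace the 80% by the fixed-time power: about 73–76% with 38 patients or 77–79% with 42. In either case say which patients count for PFS.

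The cost is a sentence or two, and either a longer stated duration or a slightly lower stated power. No extra patients are needed. No new visits are needed for men on treatment, since treatment runs to progression and the calendar already extends beyond the time required.

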14.3. Analysis of Secondary Endpoints

Secondary clinical endpoints will include toxicity, overall survival, time to PSA progression, objective response rate and PSA response rate.

We will monitor toxicities experienced by all treated patients on the study. With 42 patients, the maximum width of a 90% CI for a given toxicity rate is 27%. The probability of observing at least one rare severe toxicity (true rate=5%) is 88%.

Objective and PSA response will be estimated as the number of responders divided by the total number of evaluable patients. Exact binomial confidence intervals will be calculated for the true response proportion.

Distribution of overall survival defined as the time from registration to death due to any cause will be estimated using Kaplan-Meier methods. PSA progression will be defined according to the recommendations of PCWG2¹⁵.

14.4. Reporting and Exclusions

Any patients who withdraw consent prior to receiving a single dose of study drug will not be counted toward accrual, and will not be considered evaluable for toxicity or response.

Patients who withdraw consent from the study prior to reaching the first on-study disease assessment (after 2 cycles) will not be considered evaluable for response.

- 14.4.1 **Evaluation of toxicity.** Any participant who receives one or more doses of study drug will be evaluable for toxicity.
- 14.4.2 **Evaluation of response.** All participants included in the study must be assessed for response to treatment, even if there are major protocol treatment deviations or if they are ineligible. However, patients who withdraw consent from the study prior to reaching the first on-study disease assessment (after 3 cycles) will not be considered evaluable for response. Participants who exhibit objective disease progression or die prior to the end of cycle 1 will also be considered evaluable.

15. PUBLICATION PLAN

The Principal Investigator holds the primary responsibility for publication of the study results. The Principal Investigator will provide any such publication to NCCN, Aveo and Astellas for review at least sixty (60) days prior to submission and also comply with any provisions regarding publication as are agreed to between the Principal Investigator's institution (Dana Farber/Partners Cancer Care, Inc.) and NCCN in the Clinical Trial Agreement related to this

study. The results will be made public within 24 months of the end of data collection. However, if a report is planned to be published in a peer-reviewed journal, then that initial release may be an abstract that meets the requirements of the International Committee of Medical Journal Editors. Authorship for abstracts and manuscripts resulting from this study will be determined according to guidelines established by the International Committee of Medical Journal Editors.

17. APPENDICES

Appendix A Performance Status Criteria

| ECOG Performance Status Scale | | Karnofsky Performance Scale | | |
|--|--|-----------------------------|--|--|
| Grade | Descriptions | Percent | Description | |
| 0 | Normal activity. Fully active, able | | Normal, no complaints, no evidence of disease. | |
| | to carry on all pre-disease performance without restriction. | 90 | Able to carry on normal activity; minor signs or symptoms of disease. | |
| 1 | Symptoms, but ambulatory. Restricted in physically strenuous activity, but ambulatory and able to carry out work of a light or sedentary nature (e.g. , light housework, office work). | | Normal activity with effort; some signs or symptoms of disease. | |
| 1 | | | Cares for self, unable to carry on normal activity or to do active work | |
| 2 | In bed <50% of the time. Ambulatory and capable of all self-care, but unable to carry out any work activities. Up and about more than 50% of waking hours. | | Requires occasional assistance, but is able to care for most of his/her needs. | |
| | | | Requires considerable assistance ar frequent medical care. | |
| 2 | In bed >50% of the time. Capable of only limited self-care, confined to bed or chair more than 50% of waking hours. | | Disabled, requires special care and assistance. | |
| 3 | | | Severely disabled, hospitalization indicated. Death not imminent. | |
| 4 | 100% bedridden. Completely disabled. Cannot carry on any | | Very sick, hospitalization indicated. Death not imminent. | |
| self-care. Totally confined to bed or chair. | | 10 | Moribund, fatal processes progressing rapidly. | |
| 5 | Dead. | 0 | Dead. | |

41

Appendix B Cytochrome P450 (CYP3A4) Inducers/Inhibitors

| Cytochrome P450 (CYP3A4) Drug interaction table | | | |
|--|-----------------|--|--|
| INHIBITORS | INDUCERS | | |
| Amiodarone | Aprepitant | | |
| Cimetidine | Barbiturates | | |
| Clarithromycin | Carbamazepine | | |
| Diltiazem | Glucocorticoids | | |
| Erythromycin | Phenobarbital | | |
| Fluvoxamine | Phenytoin | | |
| Fruit Juices or products grapefruit, Seville orange, star fruit, and pomegranate | Rifabutin* | | |
| Indinavir | Rifampin* | | |
| Itraconazole | St. John's Wort | | |
| Ketoconazole* | Troglitazone | | |
| Mibefradil | | | |
| Nefazodone* | | | |
| Nelfinavir* | | | |
| Ritonavir* | | | |
| Troleandomycin | | | |
| Verapamil | | | |
| NOT azithromycin | | | |

[figure not shown]
^{*} Asterisk denotes strong inhibition / induction.

Strong inhibition implies that it can cause a > 5-fold increase in the plasma AUC values or > 80% decrease in clearance of sensitive CYP substrates. Moderate inhibitor implies that is can cause a > 2-fold increase in the plasma AUC values or 50-80% decrease in clearance of sensitive CYP substrates. Distinction is not always categorical as interaction can vary according to conditions.

This table is a guide and additional inducers/inhibitors may be identified. Please refer to the source of this table for any updated information: http://medicine.iupui.edu/clinpharm/ddis/

Appendix C Recommended Management for Tivozanib-Related Hypertension

Figure 1 provides a guideline for treatment of hypertension (HTN); however, changes may be made at the discretion of the treating physician.

RECOMMENDED ANTI-HYPERTENSIVE MEDICATIONS

| RECOMMENDED ANTI-HITTERIENSIVE MEDICATIONS | | | | | |
|--|------------------------|--------------------------------|--------------|--|--|
| Agent | Initial Dose | Initial Dose Intermediate Dose | | | |
| Dihydropyridine (DHP) Ca | lcium Channel Blockers | | | | |
| Nifedipine XL | 30 mg po qd | 60 mg po qd | 90 mg po qd | | |
| Amlodipine | 2.5 mg po qd | 5 mg po qd | 10 mg po qd | | |
| Felodipine | 2.5 mg po qd | 5 mg po qd | 10 mg po qd | | |
| Angiotensin Converting En | zyme (ACE) Inhibitors | | | | |
| Captopril | 12.5 mg po tid | 25 mg po tid | 50 mg po tid | | |
| Enalapril | 5 mg po qd | 10–20 mg po qd | 40 mg po qd | | |
| Ramipril | 2.5 mg po qd | 5 mg po qd | 10 mg po qd | | |
| Lisinopril | 5 mg po qd | 10–20 mg po qd | 40 mg po qd | | |
| Fosinopril | 10 mg po qd | 20 mg po qd | 40 mg po qd | | |
| Perindopril | 4 mg po qd | None | 8 mg po qd | | |
| Quinapril | 10 mg po qd | 20 mg po qd | 20 mg po qd | | |
| Angiotensin II Receptor Bl | ockers | | | | |
| Losartan | 25 mg po qd | 50 mg po qd | 100 mg po qd | | |
| Candesartan | 4 mg po qd | 8–16 mg po qd | 32 mg po qd | | |
| Ibresartan | 75 mg po qd | 150 mg po qd | 300 mg po qd | | |
| Telmisartan | 40 mg po qd | None | 80 mg po qd | | |
| Valsartan | 80 mg po qd | None | 160 mg po qd | | |

po = oral administration; qd = once daily; tid = three times daily

Adapted from Kollmannsberger C, et al, CUAJ. 2007; Vol 1 (Issue 2 Suppl):S41–54.

Appendix D CTCAE v.4.0

 $\underline{http://evs.nci.nih.gov/ftp1/CTCAE/CTCAE}\underline{4.03}\underline{2010-06-14}\underline{QuickReference}\underline{5x7.pdf}$

Appendix E Medwatch Form 3500A

 $\underline{http://www.fda.gov/downloads/Safety/MedWatch/HowToReport/DownloadForms/ucm082728.pdf}$
